NDURE is a theory-based, multi-level patient navigation (PN) intervention consisting of three sessions of manualized PN with multiple intervention components that target system-(care coordination), interpersonal-(social support), and individual- (health belief model); perceived susceptibility, severity, barriers, self-efficacy) level health behavior theoretical constructs to reduce barriers to care, enhance HNSCC care delivery, and improve clinical outcomes (timely, equitable PORT). NDURE will be delivered from surgical consultation to PORT initiation (~3 months). The three NDURE navigation sessions, which are expected to take 30-60 minutes each, will coincide with the presurgical consult, hospital discharge, and 1st postoperative clinic visit, time points chosen to facilitate case identification and coordination across key care transitions.

Study Duration: NDURE Feasibility: 7 months
NDURE vs Usual Care RCT: 42 months

Participant Duration: 3 months

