4.2 RCT OF NDURE VERSUS USUAL CARE

4.2.1 OVERALL DESIGN

We will conduct a single-site, non-blinded, parallel-group, RCT of NDURE versus usual care for the management of delays and racial disparities starting PORT in adults with surgically-managed, locally advanced HNSCC. The study is designed to test the following hypotheses: 1) NDURE will result in a lower rate of delayed PORT relative to usual care (primary objective) and 2) NDURE will result in a smaller difference in PORT delay between AA and whites relative to usual care (secondary objective). The statistical plan for this between-group design analyzes the superiority of NDURE relative to usual care, although our power analysis is calculated with $\alpha = 0.1$ and $1 - \beta = 0.8$ based on the desire to emphasize power over type I error at this early stage of development (single-site pilot RCT) to ensure follow-up on promising interventions.

Upon enrollment and completion of the baseline assessments, patients will be randomized 1:1 to NDURE or usual care using a permuted block randomization method, with randomly selected block sizes of 2 or 4. Randomization, which will occur at the individual patient level, will be stratified with a 1:1 allocation ratio with strata defined by race (white, AA) and location of radiation facility (MUSC, non-MUSC) because of the known association of these variables with PORT delay^{6,33}. Furthermore, to facilitate evaluation of PORT delay rates in racial subgroups, we will oversample AAs for a final sample size of 50 white and 25 AA patients in each arm (see details in **Section 9.4.6, Sub-Group Analyses**). Given the impossibility of delivering the NDURE intervention in a non-blinded fashion, allocation concealment will be non-blinded. The study statistician ([name]) will generate the randomization schema and

randomization list. The study coordinator will implement the randomization. Randomization errors will be handled as per the modified intention-to-treat (ITT) population for the efficacy analysis.

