4.2.3.2 JUSTIFICATION FOR NUMBER, FREQUENCY, AND TIMING OF INTERVENTION CONTACTS

The three NDURE sessions, which are expected to take 30-60 minutes each, will coincide with the presurgical consult, hospital discharge, and 1st postoperative clinic visit. These time points were chosen to facilitate case identification (preoperatively; Visit 2) and coordination across key care transitions from inpatient to outpatient status at the time of hospital discharge (inpatient; Visit 3) and from surgical to radiation and medical oncology specialties (post-discharge; Visit 4). These timepoints also promote the feasibility of NDURE delivery as nearly 100% of patients attend these three visits (despite travel distance-related barriers⁴¹) since patients 1) cannot have surgery without their presurgical consult; 2) are hospitalized postoperatively; and 3) return for the 1st postoperative visit for drain/tube removal. The number of intervention contacts is justified by the need to focus the intervention to key transitions of care as described above.

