8 STUDY ASSESSMENTS AND PROCEDURES

8.1 ENDPOINT AND OTHER NON-SAFETY ASSESSMENT

Feasibility

NDURE Accrual Rate is defined as the proportion of eligible patients who enroll in NDURE

NDURE Completion Rate is defined as the proportion of enrolled patients who complete the baseline assessment, at least two NDURE intervention sessions, and the final follow-up assessment

Navigation Session Completion Rate is the proportion of NDURE navigation sessions completed by each individual

Navigator Caseload is the number of simultaneous cases (on-trial participants) being navigated by the NDURE navigator

Navigator Time Allocation (Direct) is the time (in minutes), that the NDURE navigator spends directly interacting with the patient to identify and address barriers to timely, equitable PORT

Navigator Time Allocation (Indirect) is the time (in minutes), that the navigator spends generating and enacting each Barrier Reduction Plan that is not directly interacting with the patient

Questionnaire Completion Rate is the proportion of pre- and post-treatment questionnaires completed by enrolled patients

Acceptability

Satisfaction with the Interpersonal Relationship with the Navigator Scale Score is defined as the total score of this 9-item measure of the satisfaction of the interpersonal relationship with the patient navigator. This reliable and validated measure^{30,31} has been widely used in prior studies of PN. The total score of the measure ranges from 9 (minimum) to 45 (maximum); higher scores represent a better outcome (greater satisfaction with the interpersonal relationship with the navigator).

Satisfaction with Logistical Aspects of Navigation Scale Score is defined as the total score of the 26-item measure of the satisfaction of the logistical aspects of PN. This reliable and validated measure³² has been widely used in prior studies of PN. The total score of the measure ranges from 0 (minimum) to 78 (maximum); higher scores represent a better outcome (greater satisfaction with the logistical aspects of navigation).

Clinical Outcomes

PORT Delay is defined as the initiation of PORT more than 6 weeks (42 calendar days) from the date of the definitive surgical resection. In situations in which the surgical management of the primary tumor and

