the neck are staged (i.e. occur on two different calendar days), the date of the definitive surgery for the primary tumor will be used. In situations in which an additional surgical resection is required (e.g. re-resection of positive margins to clear residual disease), the date of the earlier (i.e. attempted definitive) surgical procedure will be used to determine the date of definitive surgical resection.

Time-to-PORT (TTP) is defined as the time, in days, between the date of definitive surgical resection to the initiation of PORT. All of the criteria used to adjudicate the date of the definitive surgical procedure described for the primary outcome measure will be applied to this measure.

Barriers to Care

Rate of barrier resolution is defined as the proportion of confirmed barriers (as determined by the navigator log) that are resolved during the NDURE intervention.

Unresolved barriers are the number of confirmed barriers (as determined by the navigator log) that are not resolved during the NDURE intervention.

Cancer Care Delivery Processes

Pre-Surgical Radiation Consultation is defined as the attendance by the patient at a consultation with a radiation oncologist (at MUSC or elsewhere) prior to surgery to discuss RT in the definitive or adjuvant setting

Pre-Radiation Therapy Dental Extractions is defined as the extraction of teeth prior to discharge from the index hospitalization for the definitive surgical procedure. Patients who are edentulous are not evaluable for this measure.

Surgery to Pathology Report <= 7 days is defined as the production of the pathology report from the definitive surgical procedure within the EMR within 7 calendar days of the definitive surgical procedure. Addenda to the pathology report at the request of the HNSCC team (e.g. tumor p16 status) are not counted in this measure.

Surgery to PORT Referral <= 10 days is defined as the placement of a referral for PORT, at MUSC or elsewhere, within 10 calendar days of the definitive surgical procedure.

RT Referral to Consult <= 10 days is defined as the evaluation of the patient at a postoperative consultation with a radiation oncologist within 10 calendar days of the referral being placed (or postoperative appointment being scheduled in cases in which care has been established and the return visit is no longer a consultation). The consultation may occur in the clinic or the hospital depending upon clinical circumstances.

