Change from baseline in Communication & Attitudinal Self-Efficacy Scale (CASE)-Cancer score is defined as the change in CASE-Cancer Score from baseline. The CASE-Cancer is a validated, psychometrically sound 12-item scale that addresses three domains of self-efficacy in cancer care (understanding and participating in care, maintaining a positive attitude, and seeking and obtaining information)⁵³. The CASE-Cancer scale has been used extensively in PN studies to measure perceived self-efficacy^{10,44,52}. Responses are on a 4-point Likert scale from 'Strongly disagree' (1) to 'Strongly Agree' (4). Higher scores indicate greater levels of self-efficacy in cancer care.

Navigator Barrier Log will measure 1) the number of barriers identified in the BRP during NDURE; and 2) the type of barrier in our modified version of existing PN logs^{11,44,51}

Covariates

Behavioral Risk Factor Surveillance Survey (BRFSS) Demographics. The BRFSS is the nation's premier health-related survey that collects data about health-related risk behaviors from US residents. The demographic section from the BRFSS will be used (in-person) to ascertain participant sex, age, race,

marital status, insurance, educational attainment, living situation, zipcode, phones for personal use, employment, and annual household income⁵⁴.

BRFSS Tobacco Use and Alcohol Consumption. The tobacco use and alcohol consumption sections of the BRFSS will be used (in-person) to characterize total cigarette exposure, current cigarette use, quit attempts, days of alcohol consumption, average drinks/day, frequency of ≥ 5 drinks, and maximum number of drinks.

Clinical and Oncologic Characteristics. Clinical characteristics will include comorbid medical conditions (as defined by the ACE-27⁵⁵, which ranks the severity of each of a patient's comorbidities from 0-3 and gives an overall comorbidity score based on the patient's highest comorbidity score for any individual type of ailment, with 3 indicating severe comorbidity) and cancer history. Oncologic characteristics will include HNSCC tumor subsite, HNSCC tumor histology, p16/human papillomavirus (HPV) tumor status, American Joint Committee on Cancer TNM Class and overall stage grouping, type of ablative surgery, type of reconstruction, treatment dates, facility of planned adjuvant therapy, and adjuvant treatment type planned (adjuvant radiation or chemoradiation).

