9.3 POPULATIONS FOR ANALYSES

For the efficacy analysis, we will utilize a modified ITT population. Participants will be part of the modified ITT population as defined by the following criteria:

1. Randomized to NDURE or Usual Care
2. Receipt of curative intent surgery at MUSC
3. Indication for PORT (with or without concurrent chemotherapy) per NCCN Guidelines based on the presence of at least one of the following adverse features on final pathologic evaluation: ENE, positive margin, pT3 or pT4 primary, at least pN1 nodal disease (per AJCC 8th edition for p16-ve

non-oropharyngeal SCC or AJCC 7th edition for p16+ve oropharyngeal SCC), nodal disease in levels IV or V, PNI or LVI

The modified ITT analytic population addresses the fact that eligibility, registration, randomization, and delivery of a portion of the intervention (NDURE or Usual Care) occur prior to definitive treatment of the HNSCC. However, the primary study objective (and endpoint) are defined and evaluable only for patients who undergo surgery for HNSCC and have an indication for adjuvant therapy (which can only be definitively known following surgical resection). Therefore, we expect that a predictable subset of patients will be enrolled in the study, based on meeting all inclusion, be randomized to NDURE or Usual Care, receive a portion of the intervention (NDURE Visit 1) and then subsequently develop a study exclusion criterion based on interval information that becomes available later in the clinical course that cannot be known at the time of study enrollment and registration, namely:

- failure to undergo curative intent surgery at MUSC (exclusion criteria #4)
- lack of indication for PORT (with or without chemotherapy) per NCCN Guidelines (exclusion criteria #5)

As such, patients who meet study inclusion criteria but subsequently develop exclusion criteria #4 or #5 during the course of the study will be replaced since the primary endpoint is anchored to findings that occur after analysis of the pathologic specimen obtained during surgery. Patients in the modified ITT population for whom the primary endpoint is not evaluable due to loss to follow-up will be considered navigation failures, and their time to PORT will be treated as exceeding 6 weeks for the purposes of analysis.

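### Both PORT clocks and the efficacy set depend on surgery, which follows randomisation and NDURE session 1, and no planned analysis would show by-arm differences in who reaches surgery or when

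*Combined protocol and SAP*

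**What the plan says.** **Order of events.** Section 4.2.1: "Upon enrollment and completion of the baseline assessments, patients will be randomized 1:1 to NDURE or usual care". The Schedule of Activities puts randomisation at Visit 1 and the first delivery of NDURE or usual care at Visit 2, before the operation. Section 4.2.3.2 says the three sessions "will coincide with the presurgical consult, hospital discharge, and 1st postoperative clinic visit". Under Section 6.1.1.1, the navigator both draws up the barrier reduction plan and begins acting on it at session 1. The synopsis gives the whole span: "NDURE will be delivered from surgical consultation to PORT initiation".

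**Clocks.** Section 8.1 defines PORT delay as "initiation of PORT more than 6 weeks (42 calendar days) from the date of the definitive surgical resection" and TTP as "the time, in days, between the date of definitive surgical resection to the initiation of PORT". Both start at surgery.

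**Efficacy set.** Criterion 2 of the modified ITT population in Section 9.3 is "Receipt of curative intent surgery at MUSC"; criterion 3 is a PORT indication on final pathology. The per-protocol set is a subset of this population. Sections 7.2, 9.2.2 and 9.3 say that patients failing either criterion are replaced. Section 7.2 names two expected routes out before surgery: choosing nonsurgical treatment, and choosing treatment elsewhere.

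**A presurgical process compared between arms.** Section 8.1: "Pre-Surgical Radiation Consultation is defined as the attendance by the patient at a consultation with a radiation oncologist" before surgery. The definition covers discussion of radiation as definitive as well as adjuvant treatment.

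**Data available.** The Section 8.1 covariates include "treatment dates, facility of planned adjuvant therapy", and Section 7.2 records reasons for discontinuation on the eCRF.

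**The concern.** Every planned efficacy analysis conditions on an event that happens after the intervention has begun. Randomisation therefore protects the comparison only if session 1 affects neither who has surgery at MUSC nor when.

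The analysis-set route is the better grounded of the two. Section 9.3 treats failure to have surgery at MUSC in the same way as the pathology finding, as information that emerges later. Pathology is a fact about the tumour that navigation can hardly alter. Whether to have surgery, and where, is a decision taken after session 1 with the allocation known. If NDURE raises the rate of presurgical radiation consultation, where definitive radiation may be discussed, the mix of patients reaching surgery could differ between arms.

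The date route is simpler. If surgery dates differed by arm, the surgery-to-PORT interval would change with no patient starting PORT on a different day. If surgery and PORT both slipped equally, the endpoint would not change and the longer total wait would go unseen.

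Section 4.2.2 expects this pilot to supply effect-size estimates for a definitive phase III trial, so it matters whether an observed gain means that PORT started sooner.

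**Working it through.** **Inputs from the protocol.** Section 9.2.2: 45% delay under usual care, 25% under NDURE, 75 evaluable per arm, two-sided alpha 0.10, stated power 83%, 170 enrolled to yield 150. Section 4.2.4: fewer than 9% start PORT more than 12 weeks (84 days) after surgery.

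**The plan's own figure.** Power = Φ{[δ − 1.645·√(2·p̄·(1−p̄)/n)] / √[(p₁(1−p₁)+p₂(1−p₂))/n]}. With δ = 0.20, p̄ = 0.35 and n = 75: (0.20 − 1.645 × 0.0779) / 0.0762 = 0.944, and Φ(0.944) = 82.7%. The stated 83% is reproduced.

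**Route 1: surgery later, PORT dates unchanged, no other effect.** Assume lognormal time to PORT with P(T > 42) = 0.45 and P(T > 84) = q, for q = 3%, 5% and 9%.

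- σ = ln 2 / (z₁₋q − 0.1257) and μ = ln 42 − 0.1257σ.
- A shift of s days in every NDURE patient gives a delay rate of P(T > 42 + s).
- For q = 5%: σ = 0.6931 / (1.645 − 0.126) = 0.456, median 39.7 days, and P(T > 49) = 32.1%.

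| Shift in NDURE arm | q = 3% | q = 5% | q = 9% | Fall from 45% (points) | Chance of a significant result favouring NDURE |
|---|---|---|---|---|---|
| 5 days, all patients | 34.1% | 35.5% | 37.3% | 7.7 to 10.9 | 26 to 41% |
| 7 days, all patients | 30.3% | 32.1% | 34.6% | 10.4 to 14.7 | 38 to 60% |
| 7 days, one quarter | 41.3% | 41.8% | 42.4% | 2.6 to 3.7 | 10 to 12% |

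The last column is an exact enumeration of the unstratified pooled z test, 75 per arm, at the two-sided 0.10 used for sizing; the nominal chance in that direction is 5%. An average shift of about 10 to 15 days in every patient would be needed to produce the full 20 points.

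**Route 2: selection into the modified ITT set.** 170 enrolled for 150 evaluable is 85 randomised and 10 lost per arm. Assume no true effect, and usual-care losses unrelated to delay. If a share d of the 10 NDURE losses would have been delayed, the retained rate is (85 × 0.45 − 10d) / 75.

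- d = 60%: (38.25 − 6) / 75 = 43.0%, a fall of 2.0 points; chance favouring NDURE 8%.
- d = 75%: (38.25 − 7.5) / 75 = 41.0%, a fall of 4.0 points; chance 13%.
- d = 100%: (38.25 − 10) / 75 = 37.7%, a fall of 7.3 points; chance 24%.

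The 10 losses include patients without a PORT indication, so the share due to no surgery at MUSC is smaller. On the other side, Section 9.2.2 describes the inflation as 17%, whereas 170/150 is 13.3%. With 15 losses of 85, the extreme case is (38.25 − 15) / 70 = 33.2%, a fall of 11.8 points.

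**The case against.** The strongest reply is that no mechanism is documented. No section says the navigator schedules or postpones surgery. Session 1 coincides with a consult that patients need for surgery anyway, its plan addresses barriers to timely PORT, and the component table in Section 6.1.1.1 does not list a presurgical radiation consult. Navigation could equally bring surgery forward, which would count against NDURE. All of this stands, and it is why direction and size must be called unknown.

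Second, the surgery anchor is deliberate. Section 2.2.2 names surgery-to-PORT as the critical period and the only timeliness element in the guideline. This stands: the endpoint is not an error.

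Third, holding the PORT date fixed while surgery slips goes against the pathway in Section 8.1, where the pathology report, PORT referral and postoperative consult all follow surgery. If PORT does keep its date, the postoperative pathway has been shortened. This stands as a reason to read the Route 1 figures as upper values for a given shift. It does not show whether patients wait less from randomisation.

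Fourth, Sections 9.2.2 and 9.3 disclose and justify the exclusions. Disclosure does not supply a by-arm comparison. Counting loss to follow-up as delay does not help either, because that rule covers only patients already in the modified ITT set.

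**Conclusion.** The structural point holds. The clocks and the efficacy set both depend on surgery, surgery follows randomisation and session 1, and the plan has no randomisation-anchored time, no analysis of all randomised patients and no comparison of exclusions by arm. A difference between arms in reaching surgery, or in its date, would go unseen.

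A reader might go further and infer that NDURE delays surgery, so that a positive result would be an artefact. The documents do not support that. A reader might also infer that a one-week slip explains nearly the whole 20-point target. A normal model with SD 14 days does give 18.4 points at 7 days, but it needs the slip in every NDURE patient and puts only about 0.1% of patients beyond 84 days, a very thin tail for a group Section 4.2.4 discusses as needing censoring. The skewed model gives 10 to 15 points for the same slip, and 3 to 4 points if a quarter of patients slip. Selection of 10 of 85 gives 2 points when 60% are delay-prone and 7.3 at most.

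The lognormal shape, the shifts and the delay-prone shares are assumptions. The figures show that the question is worth measuring, not that bias is present. This is an inexpensive improvement to a pilot, not a fault in its primary endpoint.

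**What to change.** Keep the primary endpoint and the modified ITT analysis. Add to Sections 9.3 and 9.4.3.2:

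1. Days from randomisation to definitive surgery by arm, as an estimate with a confidence interval.
2. Days from randomisation to PORT start by arm, as a supportive analysis in all randomised patients except those whose final pathology shows no PORT indication. Handle nonsurgical treatment as a competing event, or count it as not started through follow-up. Do not censor these patients at last contact: many will never start PORT, and censoring comes close to excluding them.
3. Counts of modified ITT exclusions by arm and reason, with exclusion criteria 4 and 5 shown separately.
4. A sensitivity analysis of PORT delay that keeps exclusion-4 patients in their randomised arm and counts them as delayed.

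Report these beside the primary result as aids to interpretation. Do not make the primary reading depend on time to surgery being no longer with NDURE: without a margin, and with no true difference, NDURE would look longer about half the time by chance.

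**Cost.** SAP wording and a little more analysis, since treatment dates and discontinuation reasons are already recorded. PORT dates will be missing for some patients treated elsewhere, particularly as Section 7.2 allows them to be discontinued, and PORT indication is unknown without surgery. Item 4 is diluted by design. If all 10 losses per arm were counted as delayed, the rates would be (33.75 + 10)/85 = 51.5% and (18.75 + 10)/85 = 33.8%, with power about 76%, so it should stay a sensitivity analysis.

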3 OBJECTIVES AND ENDPOINTS

Table 1. Study Objectives and Endpoints

OBJECTIVES	ENDPOINTS
NDURE FEASIBILITY STUDY	
Primary	
To assess the feasibility of NDURE among white and AA HNSCC patients.	NDURE Accrual Rate NDURE Completion Rate NDURE Session Completion Rate Questionnaire Completion Rate
Secondary	
To assess the acceptability of NDURE to white and AA HNSCC patients and HNSCC providers.	Patient Satisfaction with the Interpersonal Relationship with the Navigator Scale Score Patient Satisfaction with Logistical Aspects of Navigation Scale Score
To determine the feasibility of a single dedicated navigator to manage a caseload of patients for the NDURE intervention	Navigator Caseload Navigator Time Allocation (Direct) Navigator Time Allocation (Indirect)
To evaluate the feasibility of collecting pre- and post-NDURE intervention outcome measures in this patient population	Study questionnaire completion rate
RCT of NDURE VERSUS USUAL CARE	
Primary	
To evaluate the preliminary clinical impact of NDURE compared with UC on delays starting PORT among white and AA HNSCC patients.	PORT Delay Time-to-PORT (TTP) Initiation
Secondary	
To evaluate the preliminary clinical impact of NDURE compared with UC on racial disparities in delays starting PORT among white and AA HNSCC	PORT Delay TTP Initiation

Table 1. Study Objectives and Endpoints

OBJECTIVES	ENDPOINTS
patients.	
To assess the preliminary clinical impact of NDURE compared with UC on barriers to care	Barriers Resolution Rate Unresolved barriers
To determine the preliminary clinical impact of NDURE compared with UC on cancer care delivery processes	Pre-surgical Radiation Consultation Pre-RT Dental Extractions Surgery to Pathology Report \leq 7 d Surgery to PORT Referral \leq 10 d RT Referral to Consult \leq 10 d RT Consult to Initiation \leq 21 d
To evaluate the preliminary behavioral mechanism of action of NDURE	Care Transition Measure-15 (CTM-15) Score Change from Baseline in Interpersonal Support Evaluation List-12 Scale Score Change from Baseline in Perceived Susceptibility Scale Scores Change from Baseline in Illness Perception Questionnaire-Revised (IPQ-R) Consequences Sub-Scale Score Change in Baseline from Perceived Barriers Scale Change in Baseline from Communication & Attitudinal Self-Efficacy Scale (CASE)-Cancer Score

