6 STUDY INTERVENTION

6.1 STUDY INTERVENTION ADMINISTRATION

6.1.1 STUDY INTERVENTION DESCRIPTION

6.1.1.1 NDURE

NDURE is a theory-based, multi-level PN intervention consisting of three sessions of manualized PN with multiple intervention components that target system- (care coordination), interpersonal- (social support), and individual- (HBM; perceived susceptibility, severity, barriers, self-efficacy) level health behavior theoretical constructs to reduce barriers to care, increase HNSCC care delivery, and improve clinical outcomes (timely, equitable PORT). The NDURE intervention components and targeted theoretical constructs are outlined in **Table 2**. NDURE will be delivered from surgical consultation to PORT initiation (~3 months). The three NDURE navigation sessions, which are expected to take 30-60 minutes each, will coincide with the presurgical consult, hospital discharge, and 1st postoperative clinic visit, time points chosen to facilitate case identification and coordination across key care transitions. The preferred method for delivering NDURE is face to face. However, due to changes in healthcare delivery necessitated by COVID-19 pandemic, it is permissible for the NDURE navigator to use a telemedicine videoconferencing platform for NDURE sessions 1 or 3 (study visit 2 or 4). Contact beyond the three prescribed sessions will occur with a frequency and modality (e.g. text message, email, etc.) dictated by patient and navigator need. During the first session, the navigator will 1) elicit barriers and facilitators to timely PORT from the patient, caregiver, and provider, 2) develop the personalized barrier reduction plan (BRP), review it with the patient, caregiver, and provider, and 3) implement the BRP. At the two subsequent sessions, the navigator will review and update the BRP in an iterative, dynamic fashion, identifying new barriers and systematically tracking resolution of prior barriers until the start of PORT. The Navigator Manual

Table 2. NDURE Intervention Components

Component	Description	Theoretical Target
Clinical Tool		

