6.1.2 ADMINISTRATION AND/OR DOSING

6.1.2.1 NDURE

NDURE will be delivered in one-on-one, face-to-face sessions between the navigator and the participant in a clinic- or hospital-based setting. The NDURE intervention consists of three navigation sessions (Study Visits 2-4), which are expected to take 30-60 minutes each. The NDURE sessions (Study Visits 2-4) will coincide with the presurgical consult, hospital discharge, and 1st postoperative clinic visit (see **Section 1.3, Schedule of Activities**). These time points were chosen to facilitate case identification and coordination across key care transitions. Contact beyond the three prescribed sessions will occur with a frequency and modality (e.g. text message, email, etc.) dictated by patient and navigator need. The NDURE intervention will be delivered in the following settings: the MUSC Head and Neck Tumor Center and MUSC hospital. A single dedicated navigator with no competing clinical or administrative responsibilities outside of this trial will deliver the NDURE intervention. Full dose of the NDURE intervention will consist of completing all three navigation sessions. Because the administration schedule and dose of usual care is highly variable, the NDURE intervention will not be dose-matched to usual care on intensity, duration, and/or frequency. Participants in the trial are permitted to interact with other participants after randomization, regardless of treatment allocation. Such encounters may occur in waiting rooms before or after clinic appointments given the single-site design of the trial.

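### Two of the six care-process endpoints include patients whose result navigation cannot or should not change (radiation consult already held at randomization; no extraction indicated), which dilutes the arm difference without biasing it

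*Combined protocol and SAP*

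**What the plan says.** Section 3 lists six endpoints under the secondary RCT objective "To determine the preliminary clinical impact of NDURE compared with UC on cancer care delivery processes". Two are at issue here, both defined in section 8.1 under Cancer Care Delivery Processes.

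- **Dental.** The measure is met by "extraction of teeth prior to discharge from the index hospitalization for the definitive surgical procedure. Patients who are edentulous are not evaluable for this measure". No other group is removed, and no condition requires that extraction was indicated.
- **Consult.** The measure is "attendance by the patient at a consultation with a radiation oncologist (at MUSC or elsewhere) prior to surgery to discuss RT". The window closes at surgery and has no opening date. Visits about RT as primary treatment qualify as well as visits about PORT.

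On timing, section 4.2.1 states: "Upon enrollment and completion of the baseline assessments, patients will be randomized 1:1 to NDURE or usual care". The Schedule of Activities (section 1.3) puts randomization at Visit 1. Section 6.1.2.1 states: "The NDURE sessions (Study Visits 2-4) will coincide with the presurgical consult, hospital discharge, and 1st postoperative clinic visit". Section 6.1.1.1 adds: "During the first session, the navigator will 1) elicit barriers and facilitators to timely PORT from the patient, caregiver, and provider", after which the barrier reduction plan is drawn up and put into effect at that same session.

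Section 9.4.3.2 summarizes these endpoints as frequency and percent and compares arms by chi-square or Fisher's exact test in the modified ITT population. It adds no rule on dental need or consult date, and dental need is not among the clinical covariates in section 8.1.

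**The concern.** A process measure should count patients in whom the process was both applicable and still open to influence. The protocol applies that principle to edentulous patients but not to dentate patients with no indication for extraction. A dentate patient who was evaluated and needed nothing has had the intended process and is scored as not met, while an unneeded extraction is scored as met. A higher dental rate is therefore not clearly better.

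For the consult measure, a visit held before Visit 1 is a baseline characteristic, yet it counts as an outcome. The documents make such visits plausible. Surgery and PORT must already be deemed likely at screening (section 5.1), consults about definitive RT count, and radiation facility location is a stratification factor, so it must be known or presumed at randomization. They do not show how common such visits are.

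At stake is how well the pilot describes the care processes that NDURE changes. Diluted differences on these two measures could be taken as weak effects when a larger trial is designed.

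**Working it through.** **The plan's own figure.** The documents state no rate, effect or power for these two endpoints. The only stated power is for PORT delay: 75 per arm, 45% versus 25%, two-sided alpha 0.10, 83% (section 9.2.2). The pooled normal approximation used below gives 82.7%, so the method agrees with the plan's calculation, although that figure does not bear on this point.

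**Formulas.** Let pU and pN be the usual-care and NDURE rates among patients whose result can change.

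- Consult: with share c already consulted, the observed rate is c + (1 − c)p, so the difference is (1 − c)(pN − pU).
- Dental: with share q of dentate patients needing extraction (and no unneeded extractions), the observed rate is q·p, so the difference is q(pN − pU).
- Power = Φ{[d − 1.96·√(2p̄(1 − p̄)/n)] / √([pU(1 − pU) + pN(1 − pN)]/n)}, with the observed rates in place of pU and pN for the as-written endpoint. Alpha is two-sided 0.05, the general rule in section 9.4.1.

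**Consult illustration.** Assumed: 40% versus 60% among those not yet consulted; 75 per arm.

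| c (assumed) | Observed difference | Power as written | Power among those not yet consulted (n per arm) |
|---|---|---|---|
| 0 | 20 points | 69% | 69% (75) |
| 0.2 | 16 | 52% | 59% (60) |
| 0.4 | 12 | 36% | 47% (45) |
| 0.6 | 8 | 23% | 34% (30) |
| 0.8 | 4 | 13% | 19% (15) |

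Example, c = 0.4: 0.4 + 0.6 × 0.4 = 64% versus 0.4 + 0.6 × 0.6 = 76%. With n = 75, (0.12 − 1.96 × 0.0748)/0.0742 = −0.36, giving 36%.

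**Dental illustration.** Assumed: 60 of 75 per arm dentate; 50% versus 70% extracted before discharge among those in need.

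| q (assumed) | Observed difference | Power, all dentate (n = 60) | Power, those in need (n per arm) |
|---|---|---|---|
| 0.25 | 5 points | 12% | 20% (15) |
| 0.5 | 10 | 22% | 35% (30) |
| 0.75 | 15 | 38% | 49% (45) |
| 1 | 20 | 61% | 61% (60) |

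A larger assumed effect (40% versus 70%) shows the same pattern. At q = 0.3, 0.5 and 0.7 the observed differences are 9, 15 and 21 points. Power is 26%, 45% and 66% as written, against 44%, 65% and 80% among those in need.

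**A denominator to avoid.** The gains in the dental table require that need is identified equally in both arms. Suppose the denominator were instead patients whose dental evaluation recommended extraction, and navigation works by getting patients evaluated. Assume that, among those in need, 50% (usual care) and 87.5% (NDURE) are evaluated, and 80% of those evaluated have the extraction. The true rates are 0.50 × 0.80 = 40% and 0.875 × 0.80 = 70%. The restricted endpoint shows 80% in both arms, and a 30-point effect disappears.

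**The case against.** The best defence is that nothing here is biased. Need for extraction and a consult held before randomization are settled before the arm is assigned, so they balance on average and the comparison in section 9.4.3.2 is valid as written. The plan sets no target rate, does not call non-extraction poor care, and claims no power for these measures; the pilot is powered only for PORT delay. If few patients have seen radiation oncology by Visit 1, the consult half of the point is negligible. All of this stands, and it limits the point to a minor one.

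A reader might infer something stronger: that both endpoints measure things NDURE cannot change. The documents do not support that. Session 1 is before surgery and puts the barrier reduction plan into effect; the consult window runs on to surgery and the dental window to discharge. Navigation can prompt a consult or arrange extractions in either window. The difference is forced to zero only if q = 0 or c = 1.

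The defence does not reach the definitions themselves. No other section adds an indication criterion or a start date, and validity of the comparison does not make the dental percentage interpretable.

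**Conclusion.** The point holds as one of dilution and interpretation. As defined, the arm difference is the effect among patients open to influence, multiplied by (1 − c) for the consult measure and by q for the dental measure, and the dental percentage mixes dental health with care delivery. Those multipliers follow from the definitions, the dental one on the simplification that no unneeded extractions occur. The size does not follow from the documents: c, q, the dentate share and every rate in the tables are assumptions, and the loss could be small or large. Nothing supports a claim of bias between arms. Two of six secondary process measures are affected; the primary endpoint, time-to-PORT and the sample size are not.

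**What to change.** In section 8.1:

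1. **Consult.** Record the consult date. Treat patients whose radiation consult predates randomization as not evaluable (a baseline status) and compare arms among the rest. Because this status is fixed before assignment, the restriction keeps the randomized comparison.
2. **Dental.** Choose one definition that does not make the denominator depend on an evaluation after randomization:
   - restrict to dentate patients whose need for extraction was established before randomization or is judged without knowledge of arm; or
   - keep all dentate patients and count the measure as met when a pre-RT dental evaluation and any extractions it recommended were completed before discharge.

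Make the choice before outcomes are seen by arm. The rates as now defined can be reported alongside.

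The cost is a wording change, two more chart fields (consult date and dental evaluation result) and, for the restricted versions, smaller denominators. The second dental option keeps the full dentate denominator but becomes a composite of evaluation and extraction, and should be labelled as such.
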